Abbreviations: Clinical Global Impression of Change (CGI-C); Columbia-Suicide Severity Rating Scale (C-SSRS); electrocardiogram (ECG); End of Study (EoS); Early Termination (ET); Follow-up (F/U); Huntington Disease Quality of Life Questionnaire (HDQoL); Open-label Extension (OLE); Physical Examination (PE); Problem Behaviors Assessment—Short Form (PBA-s); Symbol Digit Modalities Test (SDMT); Stroop Word Reading (SWR); Total Functional Capacity (TFC); Total Motor Score (TMS); Unified Huntington Disease Rating Scale (UHDRS); Visit (V); women of childbearing potential (W●CBP).

Table Footnotes:

[figure not shown]
[figure not shown]
- The OLE VI is the same as Main Study V8 (or V7/W65 for the last group of participants in the Main Study). Assessments do not need to be repeated if conducted as part of the Main Study.
- A participant who discontinues study drug at any point during the OLE, must also be withdrawn from the study and attend an EoS visit.
- In-clinic visit window can be expanded to ±28 days; this applies to all in-clinic visits including OLE V1-4+ and OLE F/U. The expansion of the in-clinic visit window is only in case of a global pandemic.
- Collect blood after ECG is administered (not before).
- Urinalysis will be done as part of Main Study V8, not as part of OLE
- Triple ECG pre-dose.
- Single ECG 1-2 hours post-dose.
- Single ECG pre-dose.

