7.2. Discontinuation of Study Drug

In rare instances, it may be necessary for a participant to permanently discontinue (definitive discontinuation) study drug. A participant may discontinue study drug for reasons including but not limited to:

- AE
- Death
- Lost to follow-up
- Non-compliance with study drug
- Physician decision
- Pregnancy
- Protocol deviation
- Study terminated by Sponsor
- Withdrawal of consent by participant
- Loss of capability to consent

The reason for participant discontinuation from the study drug will be recorded in the eCRF.

Participants who are **discontinued from study drug** during the Main Study will be encouraged to continue their participation in the study and perform all the scheduled visits and assessments, while off study drug. If participants are unable/unwilling to attend in-clinic visits, these visits can be replaced with virtual phone visits except for the following: Main Study Week 65, Week 78/EoS and ET visits. If a clinic visit is replaced by a virtual visit at Week 4, Week 26, Week 39, and Week 52, the UHDRS-TFC, clinical laboratories, and vital signs should not be assessed (refer to Appendix 10, Section 10.10). They will continue to be closely monitored by the Investigator and will be referred for psychiatric evaluation per the Investigator's medical judgment. Participants who are discontinued from study drug during the OLE will be withdrawn from the study and will be requested to return to an EoS visit.

See the SoA (Table 2 – Main Study, and Table 3 – OLE) for data to be collected at the time of study drug discontinuation and follow-up and for any further evaluations that need to be completed.

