5.4. Data Presentation Conventions

Continuous variables (e.g., age) are summarized using descriptive statistics (the number of participants with available data, the mean, SD, first quartile (Q1), median, third quartile (Q3), minimum and maximum). Categorical variables (e.g., race) are summarized using counts and percentages. Percentages are calculated using the total participants per treatment group with available data (overall or within relevant subgroup when appropriate). Summaries for discrete variables will include frequencies and percentages. Unless obvious, denominators used for computation of percentages will be indicated in footnotes on tables.

The following conventions will be applied to all data presentations and summaries.

- For continuous variables, all mean, Q1 (25th percentile), median and Q3 (75th percentile) values are formatted to one more decimal place than the measured value. SD values are formatted to two more decimal places than the measured value. Minimum and maximum values are presented with the same number of decimal places as the measured value. This rule may be modified to fit data in a given table as long as the data displays relevant decimal places for interpretation of results.
- For categorical variables, the number and percentage of responses are presented in the form XX (XX.X%) where the percentage is in the parentheses and will be rounded to one decimal place.
- Date variables are formatted as DDMMYYYY for presentation. Time is formatted in military time as HH:MM for presentation.
- Wherever possible, data will be decimal-centered, or left aligned as appropriate to best display the data and column headers. Parentheses will also be aligned appropriately for best display. This will be detailed in the mock shells.
- P-values, if applicable, will be presented to 4 decimal places. If the p-value is less than 0.001 then it will be presented as <0.001. If the rounded result is a value of 1.000, it will be displayed as >0.999.
- Summaries of clinically significant abnormal values will include all post-baseline values (including scheduled, unscheduled, and ET visits).
- Unless otherwise stated, any statistical tests performed will use 2-sided tests at the 5% significance level.

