5.5.3. Study Day and By-Visit Summaries

If the date of interest (date of visit, date of start of medication, date of AE, etc.) occurs on or after the first dose date then study day will be calculated as (date of interest – date of first dose) + 1. If the date of interest occurs prior to the first dose date, then study day will be calculated as (date of interest – date of first dose). Study Day 1 is the date of first dose and as per CDISC Study Data Tabulation Model Implementation Guide (SDTMIG) 3.2 requirements, there is no Study Day 0.

For by-visit summaries and/or statistical models for efficacy, ET visit for a specific measure will be assigned to the next closest non-missing planned scheduled visit of this measure.

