7.7. OLE Efficacy Analyses

The final analyses of OLE data will be performed at the End of OLE when all participants complete the OLE EoS visit. Interim analyses may be performed as needed.

The OLE analysis will be presented using the following labels for treatment group, in the order displayed:

- Placebo bid (Main Study) to Pridopidine 45 mg bid (OLE)
- Pridopidine 45 mg bid (Main Study) to Pridopidine 45 mg bid (OLE)
- Total of above two groups (where applicable)

Proportion of participants with change of UHDRS-TFC from Main Study Baseline ≥ -1 by treatment group and the difference between treatment groups at each OLE visit will be provided along with a 2-sided 95% CIs using normal approximation and p-values from a logistic regression similar to that described in Section 7.4.1. This analysis will be repeated using a threshold of 0 for proportion of participants with change of UHDRS-TFC from Main Study Baseline ≥ 0 .

Summary statistics will be presented for UHDRS-TFC, cUHDRS, UHDRS-TMS, Q-Motor

[REDACTED] and Q-Motor [REDACTED]

[REDACTED] by treatment group and visit during the OLE period as described below:

- Change from Main Study Baseline and the observed values of UHDRS-TFC, cUHDRS, UHDRS-TMS, and Q-Motor measurements at each OLE visit
- Change from OLE Baseline and the observed values of UHDRS-TFC, cUHDRS, UHDRS-TMS, and Q-Motor measurements at each OLE visit

In addition, the durability of treatment response to pridopidine in the OLE period will be assessed by the proportion of participants who continue to respond to pridopidine in OLE among the responders in double-blind treatment period. Responders defined using following endpoints will be assessed for the durability:

- Change from Main Study Baseline to Week 65 in UHDRS-TFC ≥ 0 , and change from Main Study Baseline to each OLE visit in UHDRS-TFC ≥ -1
- Change from Main Study Baseline to Week 65 in UHDRS-TFC ≥ 0 , and change from Main Study Baseline to each OLE visit in UHDRS-TFC or ≥ 0
- Change from Main Study Baseline to Week 65 in cUHDRS ≥ -1 , and change from Main Study Baseline to each OLE visit in cUHDRS ≥ -1.5

- Change from Main Study Baseline ≤ 0 in UHDRS-TMS at Week 65, and change from Main Study Baseline ≤ 0 in UHDRS-TMS at each OLE visit
- Change from Main Study Baseline ≤ 0 in Q-Motor [REDACTED] and change from Main Study Baseline ≤ 0 insec in Q-Motor [REDACTED] at each OLE visit

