For the exploratory endpoints in OLE, including CGI-C, PBA-s, HDQoL, SDMT, and SWR, the summary tables of observed values and change from Baseline over time will be provided by treatment group and OLE visit.

No imputation will be performed for the OLE analyses. Analyses using external controls may be performed to contextualize the long-term effect of pridopidine on treating HD in OLE period. These analyses, if required, will be detailed in a separate SAP.

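### By-visit OLE responder proportions in SAP 7.7 lose participants who stop pridopidine after one exit value, and the durability denominator is not stated

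*SAP*

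**What the plan says.** **Endpoints.** SAP 7.7 reports the proportion with TFC change from Main Study Baseline of at least -1, repeated at 0, "by treatment group and the difference between treatment groups at each OLE visit will be provided along with a 2-sided 95% CIs". It also assesses durability as "the proportion of participants who continue to respond to pridopidine in OLE among the responders in double-blind treatment period".

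**Missing values.** The same section states that "No imputation will be performed for the OLE analyses". The general convention in SAP 5.4 is that "Percentages are calculated using the total participants per treatment group with available data".

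**Stopping drug.** Protocol 7.2 says that "Participants who are discontinued from study drug during the OLE will be withdrawn from the study". The footnote to the OLE schedule (Protocol 1.3.2, repeated in the SAP schedule) adds the exit visit: "A participant who discontinues study drug at any point during the OLE, must also be withdrawn from the study and attend an EoS visit". TFC is scheduled at that visit. For by-visit efficacy work, SAP 5.5.3 says the "ET visit for a specific measure will be assigned to the next closest non-missing planned scheduled visit of this measure".

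**Main Study contrast.** SAP 7.4.2 counts discontinuation for progression-related death or for meeting a Stopping Rule as non-response. It uses observed values after other discontinuations and imputes under MAR where there are none. SAP 7.1.1 carries a similar strategy to other binary endpoints only where that is appropriate. SAP 7.7 sets no such rule for the OLE.

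**The concern.** In the Main Study a participant can stop drug and stay under observation. In the OLE stopping drug ends follow-up. With available-data percentages and no imputation, someone who stops for an adverse event, a Stopping Rule, loss of capability to consent or non-compliance is seen once more and then vanishes from every later proportion. No rule makes that person a non-responder.

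The by-visit curve is then a curve for people still on drug. It can stay level while the number of OLE entrants still treated and responding falls. SAP 3.5.4 names durability of effect as a purpose of the OLE analyses, so this affects the quantity of interest. SAP 3.5.4 and 7.7 also allow for external-control comparisons under a separate SAP, where the same selection could matter.

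**Working it through.** **Inputs.** The documents give no OLE sample size, response rate or dropout rate, so there is no OLE figure to reproduce. The one rate available is the Main Study planning value of 22.5% (Protocol 9.2, SAP 3.3), for which 372/(1 - 0.225) = 480 checks. Using it in the OLE is an assumption.

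**Step 1: the mechanism, in an assumed cohort.** Take 100 double-blind responders. Ten stop before OLE Week 26 and ten more before Week 52. All 20 have failing exit values, and 70% of stayers respond.

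| | Week 26 | Week 52 |
|---|---|---|
| Available data, exit value mapped | 63/100 = 63.0% | 56/90 = 62.2% |
| Fixed denominator | 63/100 = 63.0% | 56/100 = 56.0% |

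The exit value removes the discrepancy at the first visit after stopping. At the next visit it is 6.2 points, and a fall from 63% to 56% looks almost flat.

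**Step 2: general form.** Let d be the share with no value at the visit, p the observed proportion and q the response among those missing. The proportion of everyone is (1 - d)p + dq, so the overstatement is d(p - q).

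- With p = 60% and q = 0: 3.0 points at d = 5%, 6.0 at 10%, 13.5 at 22.5% and 18.0 at 30%.
- With q = p: zero.
- With q ten points above p: response is understated, by 0.5 points at d = 5% and 3.0 at d = 30%.

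If the question is instead whether an entrant is still on drug and responding, q = 0 by definition. The available-data figure can then never be the lower one.

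**Step 3: illustrative size by visit.** The share remaining at t weeks is 0.775^(t/65).

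| OLE week | Remaining | Left |
|---|---|---|
| 26 | 0.903 | 9.7% |
| 52 | 0.816 | 18.5% |
| 78 | 0.736 | 26.4% |
| 104 | 0.665 | 33.5% |

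OLE visits with TFC are 26 weeks apart. If every exit value is obtained and mapped to the next visit, those absent at Week 52 left before Week 26, and those absent at Week 104 left before Week 78.

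*All leavers failures.* Relative overstatement is 1/(share with a value) - 1:
- Week 52: 1/0.903 - 1 = 11%.
- Week 104: 1/0.736 - 1 = 36%.

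*Leavers respond half as often as stayers* (proportions relative to the stayers' rate):
- Week 52: observed (0.8155 + 0.5 × 0.0876)/0.9031 = 0.9515; everyone 0.8155 + 0.5 × 0.1845 = 0.9078; ratio 1.048, about 5%.
- Week 104: observed (0.6651 + 0.5 × 0.0714)/0.7365 = 0.9515; everyone 0.6651 + 0.5 × 0.3349 = 0.8326; ratio 1.143, about 14%.

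**Step 4: does any other text close the gap?**
- SAP 7.7 takes its logistic model from Section 7.4.1. That section is the cUHDRS MMRM and has neither a logistic model nor a non-responder rule; both are in 7.4.2.
- The Kaplan-Meier and Cox analysis of time to TFC worsening keeps leavers at risk until their last assessment but then censors them, so stopping is not a failure there either.
- The OLE mITT set (SAP 4.1.2) needs at least one valid in-clinic OLE TFC. An early leaver with no exit TFC is not in the set at all.
- The durability wording, "proportion of participants who continue to respond to pridopidine in OLE among the responders in double-blind treatment period", reads naturally as a fixed denominator. The SAP 5.4 convention would restrict it to those with a value. The SAP does not say which governs.

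**The case against.** A reader might infer that the OLE proportions rest only on participants still in the extension, that the durability denominator certainly shrinks, and that response is therefore overstated. None of these is supported as stated.

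- **Exit value.** The exit TFC is collected and mapped to one visit, so a failure seen there counts once. Ignoring it would give 1/0.816 - 1 = 23% at Week 52 and 1/0.665 - 1 = 50% at Week 104, roughly twice and 1.4 times the figures above.
- **Durability wording.** It can be read as a fixed denominator, and SAP 5 defers to section-specific rules. What stands is ambiguity.
- **Direction.** Overstatement of TFC response needs leavers to do worse than stayers. That is plausible, but no document shows it.
- **Rate.** The 22.5% is borrowed. SAP 3.6.3.1 reports low discontinuation in the Main Study, and OLE entry is limited to on-treatment completers. Week 104 concerns few participants: recruitment was planned from Q3 2020 to about Q4 2021, and the OLE closes 12 months after the last double-blind completion, planned for Q1 2023, unless extended.
- **Composite rule.** Classifying someone as a non-responder is not imputing a value, and Protocol 9.4.6 ties the OLE logistic analysis to the TFC response analysis. The Main Study rule could therefore be argued to carry over. With the SAP cross-reference pointing elsewhere and SAP 7.1.1 conditional, that is not settled.
- **Other displays.** Withdrawals with reasons (SAP 6.1) and counts of missing participants (SAP 5.1) will be shown. They let a reader see the attrition but do not correct the proportion.

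These points limit the size and certainty. They do not restore leavers to the later visits.

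**Conclusion.** The point holds in a limited form. As written, the by-visit OLE TFC responder proportions drop participants who stop pridopidine from every visit after the one that receives their exit value, and no OLE rule clearly counts stopping as non-response. The durability denominator is not specified.

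Once anyone has left at an earlier visit, the available-data figure exceeds the share of OLE entrants still on drug and responding. It overstates TFC response only on the further assumption that leavers do worse than stayers.

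The sizes are illustrative: about 11% relative at OLE Week 52 and 36% at Week 104 if all leavers fail, or about 5% and 14% if they respond half as often. All four assume 22.5% dropout per 65 weeks at a constant rate and complete exit values. At 5% cumulative dropout with 60% observed response the excess is at most about 3 points.

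It would be wrong to infer that the trial's main conclusions are at risk. SAP 3.5.3 bases the submission on Main Study data with OLE results as later updates, so the primary and hierarchical tests are untouched. The change should still be made, because durability is a stated purpose of the OLE analyses.

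**What to change.** In SAP 7.7, for each OLE visit, also report the responder and durability proportions on a fixed denominator:

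- **Responder proportions:** all OLE participants whose scheduled visit falls before the administrative close of the OLE.
- **Durability:** all double-blind responders entering the OLE, with the same restriction. State that this denominator is fixed.
- **Counting:** participants who stopped pridopidine or died before the visit are non-responders. Exclude only visits that could not be reached because the OLE closed, so that staggered entry is not counted as failure.
- **Display:** show this beside the observed-case proportion, with n at each visit.

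The cost is one or two sentences and a derived flag from disposition data already collected. The downsides are a less favourable figure and a composite that treats stopping for any reason as non-response. That is stricter than the Main Study rule in SAP 7.4.2 and should be labelled as such.

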8. SAFETY ANALYSIS

8.1. General

The SP will be used for all safety analyses based on the actual treatment received. AEs and SAEs will be collected from the Screening visit through end of the study period. Safety analyses will be presented separately for the Main Study and OLE according to the set of data associated with the two portions of the study.

Safety assessments will be summarized and listed for all data collected at in-clinic or VV (planned or converted).

8.2. Duration of Exposure

Duration of exposure to study drug (days treated) is the number of days on treatment based on the first and last days of treatment with the study drug (last day of study drug – first day of study drug + 1). In addition to summarizing overall treatment exposure in weeks, the weeks of exposure using the categories <13 weeks, ≥ 13 to <26 weeks, ≥ 26 to <39 weeks, ≥ 39 to <52 weeks, ≥ 52 to <65 weeks, ≥ 65 to <78 weeks and ≥ 78 weeks will be summarized using the number and percentage of participants exposed to study drug by treatment groups. In addition to the above intervals the number and percentage of participants exposed for ≥ 13 weeks, ≥ 26 weeks, ≥ 52 weeks, ≥ 65 weeks, ≥ 78 weeks will also be summarized.

Duration of treatment (days) will also be summarized by treatment group using descriptive statistics for continuous parameters as described in Section 5.4.

8.3. Study Treatment Compliance

Treatment compliance will be calculated using the following formula:

$$\text{Compliance (\%)} = [\text{Total number of doses taken} / \text{Total number of scheduled doses}] \times 100$$

The total number of scheduled doses will be calculated based on the number of capsules planned for the days of exposure of each participant. The total number of doses taken will be calculated as the difference between capsules dispensed and capsules returned recorded for all bottles dispensed. For bottles that are lost and missing the counts of capsules returned, 50% compliance is assumed for each lost bottle (i.e., 30 capsules are taken). If a patient has completed or withdrawn from the study without returning any bottles at last visit in Main Study, 50% compliance is assumed during the period the capsules in these bottles are expected to be taken, i.e., from the bottle dispense date until the earliest of the day prior to next bottle dispensing visit, treatment completion date, or early withdrawal date. The compliance (expressed as %) will be summarized with descriptive statistics for continuous parameters by treatment group and overall.

The initial dose, titrations and Investigator-initiated dose changes that occur throughout the study as captured on the Dose Management Log and Missed Dose / Incorrect Dosing eCRF pages will be displayed in Listings.

The number and percentage of participants with compliance <80%, 80 to 100%, >100% will also be summarized by treatment group and overall.

8.4. Adverse Events

All AEs will be coded using MedDRA Version 23.0 (or a later version if updated during the study).

For statistical analysis, a TEAE is defined as an AE that occurs for the first time or worsens (as captured on the eCRF) on or after initiation of treatment in the corresponding analysis period (Main Study or OLE Treatment Period) EoS. Due to the short half-life of Pridopidine (10-12 hrs) AEs that started more than 14 days after end of treatment are not considered TEAEs.

The terms AEs and TEAEs are used interchangeably in this SAP and unless otherwise specified refer to TEAEs.

An overall summary will be presented by treatment groups that includes the number and percentage of participants who experienced at least one TEAE for the following categories: All TEAEs, serious TEAEs, TEAEs leading to study discontinuation, TEAEs leading to death, TEAEs based on maximal Severity, TEAEs leading to study drug withdrawal anytime during the study, TEAEs leading to study drug withdrawal during titration. When appropriate, a total column may appear as the last column.

Summaries will be presented for all TEAEs by SOC and PT for the following categories of TEAEs:

- TEAEs, severe TEAEs, Treatment-related TEAEs, Serious TEAEs (see below for more details), TEAEs potentially related to QT prolongation, (e.g., palpitations, dizziness, syncope, cardiac arrhythmias, and sudden death), TEAEs related to abuse potential (See Appendix 12.2 for the AE terms), TEAEs causing discontinuation from the study.

The above summaries will include the number of events as well as number and percentage of participants experiencing at least one TEAE in each SOC and PT. To count the number of participants with any TEAEs, a participant who experiences multiple TEAEs within the same SOC will be counted only once for that SOC (if the TEAEs are coded to the same PT). A participant who experiences multiple TEAEs coded to the same PT within the same SOC will be counted only once for that PT. The number and percentage of participants experiencing any TEAE will also be provided. All percentages will use the number of participants in the SP within that treatment group as the denominator. In the summaries SOCs will be sorted in descending order based on number of participants in Total column; PT within SOC will be sorted by descending number of participants in Total column.

TEAEs will also be summarized by maximal severity. Summary table will include the number and percentage of participants experiencing at least one TEAE in each SOC, PT, and severity.

The relation of TEAEs to study drug will be summarized by their relatedness (related or not related).

Listings for deaths, serious TEAEs, and TEAEs leading to discontinuation will be presented.

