8.3.1. Time Period and Frequency for Collecting AE and SAE Information

All AE and SAEs will be collected from the signing of the ICF until the last Follow-up visit at the timepoints specified in the SoA ([Table 2 – Main Study](#), and [Table 3 – OLE](#)). Assessment should be done through on-site clinic visits, safety TCs, and virtual visits (via telephone).

An event that emerged during or after treatment or worsened relative to the pretreatment state will be recorded as a treatment-emergent adverse event (TEAE).

All SAEs will be recorded and reported to the Sponsor or designee immediately upon any site study staff becoming aware and under no circumstance should this exceed 24 hours, as indicated in Appendix 3 (Section 10.3). The Investigator will submit any updated SAE data to the Sponsor within 24 hours of it being available.

Investigators are not obligated to actively seek AE or SAE after conclusion of the study participation. However, if the Investigator learns of any SAE, including death, at any time after a participant has been discharged from the hospital, and he/she considers the event to be reasonably related to the study drug or study participation, the Investigator must promptly notify the Sponsor.

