9.4.5. Safety Analyses

The safety analysis will be conducted on the safety dataset. The AEs will be coded according to the Medical Dictionary for Regulatory Activities (MedDRA) dictionary. The TEAEs will be summarized by treatment group, system organ class and preferred term. Further summaries will be done by seriousness, severity and relationship to study drug.

Vital signs, ECG data and laboratory tests at Baseline at each post-baseline visit, and changes from Baseline to each of the post-baseline visits will be summarized with descriptive statistics. Shift tables for the laboratory tests based on a classification of values as low, normal, or high with respect to the reference range will be summarized.

For ECG data, absolute QTcF of > 450 ms, > 480 ms, and > 500 ms, changes from Baseline in QTcF > 30 ms and ≤ 60 ms, and changes in QTcF > 60 ms throughout the study will be summarized.

All other safety data will be summarized with descriptive statistics.

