3.2.7. Safety Endpoints

Safety endpoints will include the following:

- Incidence of AEs and SAEs throughout the study
- Changes from Baseline and absolute thresholds as per ICH E14 in QTcF and other ECG parameter assessments throughout the study
- Change in clinical safety laboratory tests (serum/blood chemistry, hematology, and urinalysis) and summary of abnormalities throughout the study
- Changes from Baseline C-SSRS throughout the study
- Change in vital signs and summary of abnormalities throughout the study
- Abnormalities in Physical Exam
- Abnormalities in Neurological Exam

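### If 'end of treatment' in SAP 8.4 means last dose, non-fatal SAEs starting more than 14 days later in participants followed off drug enter no by-arm AE or SAE table

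*SAP*

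**What the plan says.** Protocol 8.3.1 sets the collection window: "All AE and SAEs will be collected from the signing of the ICF until the last Follow-up visit". It then defines treatment emergence without an end date: "An event that emerged during or after treatment or worsened relative to the pretreatment state will be recorded as a treatment-emergent adverse event (TEAE"). Protocol 9.4.5 plans the by-arm summary on that basis: "The TEAEs will be summarized by treatment group, system organ class and preferred term".

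SAP 3.2.7 gives the first safety endpoint as "Incidence of AEs and SAEs throughout the study".

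SAP 8.4 narrows the definition, citing a half-life of 10 to 12 hours: "AEs that started more than 14 days after end of treatment are not considered TEAEs". It adds that "The terms AEs and TEAEs are used interchangeably in this SAP and unless otherwise specified refer to TEAEs". Its overall summary and its system organ class and preferred term summaries are all specified on TEAEs, including the serious and fatal categories. On listings it says: "Listings for deaths, serious TEAEs, and TEAEs leading to discontinuation will be presented".

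Under Protocol 7.2, participants who stop drug during the Main Study are encouraged to "continue their participation in the study and perform all the scheduled visits and assessments, while off study drug". Stopping drug in the OLE means leaving the study, so the question concerns the Main Study only.

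**The concern.** The trial deliberately follows participants after they stop drug and collects their events, but SAP 8.4 appears to stop counting 14 days after the last dose. The SAP endpoint covers the whole study, while the tables meant to report it cover time on drug plus two weeks.

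At stake is a by-arm comparison of serious events that matches the primary efficacy analysis, which uses all observed values whether or not the participant is still on drug. Drug-stoppers are a selected group: Protocol 7.1 lists QT, renal, psychiatric and seizure reasons, among others. A later non-fatal serious event in one of them would be in the database but not in the SAE incidence by arm.

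**Working it through.** The documents give no figure to reproduce. The check is a trace of outputs, followed by an illustration of size.

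**Step 1: what end of treatment means.** SAP 8.4 does not define it.
- *Last dose.* The reason given for the cut is the drug's half-life, which makes sense only if the clock starts at last dose: 14 × 24 / 12 = 28 half-lives, or 14 × 24 / 10 = 33.6. SAP 5.5.6, written for participants continuing beyond Week 65, takes the last drug date from the eCRF page named End of Treatment.
- *End of the treatment period.* SAP 8.4 ties TEAEs to the Main Study Treatment Period, which SAP 5.5.7 runs from first dose to the participant's end of the Main Study, off-drug time included. On this reading the cut removes almost nothing.

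The first reading fits the rationale better. The rest of the trace assumes it.

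**Step 2: where a Main Study event would appear.**

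| Event | By-arm AE/SAE table (SAP 8.4) | Other displays |
|---|---|---|
| SAE starting up to 14 days after last dose | Yes | Serious-TEAE listing |
| Death, causal event starting up to 14 days after last dose | Yes, even if death comes later (the cut is on event start) | Deaths listing, narrative, disposition |
| Death, causal event starting later | No | Deaths listing (no TEAE limit), narrative (SAP 8.5), by-arm disposition by reason for withdrawal (SAP 6.1; death is a reason in Protocol 7.3) |
| Suicidal ideation or behavior, off drug | As an SAE, only if it starts within 14 days | C-SSRS by arm and visit, with worst and last post-baseline shifts and no 14-day limit (SAP 8.9) |
| Other non-fatal SAE starting more than 14 days after last dose | **No** | General participant listings carrying treatment group (SAP 5.1); not in the named serious-TEAE listing |

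The last row is the gap. Participants who complete on drug, or who leave when they stop drug, are barely affected, because their safety call comes 2 weeks (±5 days) after the EoS or ET visit.

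**Step 3: size.** The documents give neither the share who stop drug and stay in follow-up nor an SAE rate. Assumptions:
- 250 per arm (the SAP version log reports 499 randomized).
- Share stopping drug s = 0.10 to 0.225. The upper value borrows the planned study dropout in SAP 3.3.
- Share of stoppers staying to Week 65, r = 0.25 to 0.75.
- Mean stop at Week 32.5.
- 10 SAEs per 100 person-years.

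Uncounted person-years per arm = 250 × s × r × (65 − 32.5 − 2)/52.
- Low: 250 × 0.10 × 0.25 × 30.5/52 = 3.7, giving about 0.4 SAEs.
- High: 250 × 0.225 × 0.75 × 30.5/52 = 24.7, giving about 2.5 SAEs.

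On-drug person-years per arm, taking 70 weeks for those who do not stop, = 250 × (1 − s) × 70/52 + 250 × s × 32.5/52. This is 318.5 at s = 0.10 and 296.0 at s = 0.225. The uncounted time is therefore about 1% to 8% of on-drug time.

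Follow-up can run to Week 78. Adding 13 weeks for every stopper who stays raises the high case to 250 × 0.225 × 0.75 × 43.5/52 = 35.3 person-years, about 3.5 SAEs. The order of size is unchanged.

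**Step 4: cross-check over both arms.** Take 480 participants, uniform stop times, and every stopper followed to Week 65. Uncounted time per stopper = (65 − 2)²/(2 × 65) = 30.5 weeks. With 2% stopping (9.6 people) this is 5.6 person-years, or 0.9% of all 65-week follow-up. With 22.5% (108 people) it is 63.2 person-years, or 10.6%.

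**The case against.** A reader might infer that off-drug SAEs and deaths vanish from every by-arm display, or that a post-withdrawal imbalance in suicidality would be missed. The documents do not support either. Events starting in the first 14 days off drug are tabulated. Deaths have an unrestricted listing and appear by arm as a reason for withdrawal. The C-SSRS is tabulated by arm at all visits.

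The whole-study premise is also weaker than it looks. Protocol 3.1.1 and SAP Section 2 ask for incidence overall and by severity and relationship; only SAP 3.2.7 uses the whole-study phrase. The same list uses it for safety laboratories, which are mostly not collected off drug. The change is declared in the SAP version log with its rationale. The SAP prevails over the protocol, and its Preface says differences will be explained in the CSR.

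Finally, the size is assumed. People counted as study dropouts do not contribute off-drug follow-up, so 22.5% is generous. Protocol 7.2 expects permanent drug discontinuation to be rare, and SAP 3.6.3.1 reports low discontinuation, although that passage is about leaving the study.

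These points limit the scope and the severity. They leave the gap in place: disclosure and patient listings do not supply a by-arm incidence table for late non-fatal SAEs, and the undefined term means two programmers could produce different tables from the same text.

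**Conclusion.** The point holds in a limited form. It is conditional on end of treatment meaning last dose, which is the better-supported reading but is not stated for TEAEs. On that reading, non-fatal SAEs starting more than 14 days after last dose in participants followed off drug are collected but enter no by-arm AE or SAE incidence table. That departs from the open-ended definition in Protocol 8.3.1 and from the endpoint in SAP 3.2.7. The 14-day window itself is reasonable as an exposure window.

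The severity is minor. The loss is about 0.4 to 2.5 SAEs per arm to Week 65 under the assumed rates, probably near the low end. Numbers this small would rarely show an imbalance between arms. The case for acting is that SAEs are few, each one matters, and the correction is cheap.

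**What to change.** In SAP 8.4:
- Define end of treatment as the date of last study drug for every participant, and reconcile it with the Main Study Treatment Period in SAP 5.5.7.
- Keep the 14-day TEAE tables as they are.
- Add a by-arm summary, overall and by system organ class and preferred term, and a listing of all SAEs and deaths from first dose to the end of the Main Study, including off-drug follow-up.
- Name that summary as the report of the whole-study SAE endpoint in SAP 3.2.7.
- State that the TEAE window departs from Protocol 8.3.1.

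The data are already collected and no protocol change is needed. The cost is slightly longer output.
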